#### 5.6.4.2 Low resistance IMT training protocol

Participants in the low resistance IMT group will undertake 30 breaths, two times daily, 7 days per week, using the POWERbreathe® KHP2 at home. The training load will be set at 10% of MIP, and will remain at this level throughout. Training will continue for a minimum of two weeks and can continue until the day of surgery. Participants will also be given a usual care leaflet containing advice on deep breathing exercises.

#### 5.6.5 Telephone support

Participants in the high and low resistance IMT groups will be given telephone helpline numbers with instructions to call the research team member who trained them to use the device at their hospital if they have any queries relating to the IMT intervention. If they have difficulties with the device itself, they will also be given the technical helpline number POWERbreathe® if they have any questions relating to the IMT intervention or are experiencing problems with the device.

#### 5.6.6 SMS text reminders

Participants in the high and low resistance IMT groups who consent to receive notifications by SMS text will be sent intermittent text messages during the period of the training interventions, reminding them to perform their breathing exercises.

#### 5.6.7 Usual care protocol

Participants will be given advice about the importance of deep breathing exercises and provided with a leaflet containing written information on peri-operative deep breathing exercises. The usual care leaflet will also be given to participants in the IMT groups.

#### 5.6.8 Care procedures common to all three groups

For all participants, other aspects of pre-operative care (including advice about surgery) will be according to local protocols. Basic information about pre-operative care including prehabilitation programmes will be collected from participating sites.

#### Primary and secondary outcomes

#### Primary outcome

5.7

5.7.1 The primary outcome will be the incidence of any PPC (a yes/no binary outcome) occurring inhospital (before discharge) or hospital readmission for a PPC within 30 days from surgery in each of the three care groups. PPCs affect between 2% and 40% of patients undergoing major surgery depending on the definition used [33-35]. The variability in reporting of PPCs in the literature makes it difficult to precisely estimate the true frequency of PPCs in our patient population. We will use the composite outcome proposed by the European Society of Anaesthesiology and the European Society of Intensive Care Medicine as a consensus definition for PPC [36]. This includes respiratory failure, pulmonary infection, atelectasis, effusion, pneumothorax, aspiration pneumonitis and bronchospasm; there are specified diagnostic criteria for each component. These complications are all plausibly modified by the intervention because increased respiratory muscle strength enables patients' normal respiratory effort to exceed respiratory system compliance (typically decreased following surgery) and promote adequate pulmonary ventilation (improved gas exchange, reduced atelectasis and infection) and reduce the incidence of respiratory distress (high respiratory rate, use of accessory muscles, abnormal breathing patterns) which in turn will decrease the likelihood of respiratory failure.

This definition of PPC was used in the PERISCOPE study which reported the development of the ARISCAT tool for predicting PPCs [1]. The PERISCOPE study (prospective cohort of 5859 patients) reported a PPC frequency of 20% using this composite in a mixed surgical cohort (ARISCAT score > 26, recent personal communication) [2]. The PERISCOPE cohort included a large proportion of orthopaedic patients (20%), who are at lower risk of PPCs than patients undergoing cardiothoracic & abdominal surgery; therefore, the incidence of PPCs in our study population is likely to be higher [23].

Since funding was obtained to conduct the INSPIRE study, a new consensus definition for PPCs has been reported (Standardized Endpoints for Perioperative Medicine-Core Outcome Measures in Perioperative and Anaesthetic Care, StEP-COMPAC) [37]. However, we have kept our original definition of PPCs (see above) because this was used to estimate the event rate for the PERISCOPE cohort and was the basis for our sample size calculation.

#### 5.7.1.2 Individual elements of the composite outcome

#### i) Respiratory infection

Criteria: Treatment with antibiotics for a respiratory infection, plus at least one of the following criteria:

- New or changed sputum;
- New or changed lung opacities on a clinically indicated chest radiograph;
- Temperature >38.3°C;
- Leukocyte count >12,000/mm^3 [4, 38].

Clinical relevance: Post-operative pneumonia is common (9-40% of patients) and associated with substantial morbidity and mortality (30-46% mortality). Consequently it has face validity as a clinically important PPC.

Patient relevance: Postoperative pneumonia has patient relevance because of the associated morbidity, mortality and the association with reduced quality of life.

#### ii) Respiratory failure

Criteria: Postoperative  $PaO_2$  <60 mmHg (<8kPa) on air, a ratio of  $PaO_2$  to inspired oxygen fraction <300, or arterial oxyhaemoglobin saturation measured with pulse oximetry <90% and requiring oxygen therapy [7, 39, 40].

Clinical relevance: Respiratory failure is associated with the need for ventilation, critical care admission, and increased morbidity and mortality. It has important clinical consequences and is therefore clinically relevant.

Patient relevance: Respiratory failure is of relevance to patients as it may prolong hospital stay and increase hospital mortality and long term mortality at 5 years. Furthermore, it may result in invasive interventions such as non-invasive ventilation which may be associated with discomfort.

#### iii) Pleural effusion

Criteria: Chest radiograph demonstrating blunting of the costophrenic angle, loss of the sharp silhouette of the ipsilateral hemidiaphragm (in upright position), evidence of displacement of adjacent anatomical structures, or (in supine position) a hazy opacity in one hemithorax with preserved vascular shadows [41].

Clinical relevance: the accumulation of fluid within one, or both, pleural cavities adversely affects the mechanics of ventilation. This impairs ventilation-perfusion matching, increases work of breathing and contributes towards the development of respiratory failure (as described above).

Patient relevance: Pleural effusion is of relevance to patients as it may prolong hospital stay, and contribute towards morbidity and mortality. It increases the risk of respiratory failure and potentially necessitates interventional procedures such as intercostal chest drain placement, which is uncomfortable and associated with the risk of complications.

#### iv) Atelectasis

Criteria: Suggested by lung opacification with shift of the mediastinum, hilum, or hemidiaphragm toward the affected area, and compensatory over-inflation in the adjacent nonatelectatic lung [42].

Clinical relevance: Atelectasis commonly contributes towards the development of pneumonia and causes respiratory failure, both of which are associated with prolonged length of stay and mortality. Atelectasis is a common cause of postoperative hypoxaemia and prevention of progression to requirement for invasive mechanical ventilation has been studied in several surgical cohorts, indicating the perceived importance of this condition. Weak respiratory muscles predispose to atelectasis and therefore the benefits of inspiratory muscle training might be most sensitively appreciated through measuring rates of atelectasis.

Patient relevance: Atelectasis is commonly considered as a precursor to the development of pneumonia, commonly contributes towards respiratory failure and therefore prolongs hospital length of stay and is associated with dyspnoea, all of which are of relevance to patients.

#### v) Pneumothorax

Criterion: Air in the pleural space with no vascular bed surrounding the visceral pleura.

Clinical relevance: Air in the pleural space is similar to fluid in the pleural space in that it adversely affects the mechanics of ventilation - impairing ventilation-perfusion matching, increasing work of breathing and contributing towards the development of respiratory failure. In the peri-operative setting there is the additional concern about the cause of the pneumothorax, as it may represent a complication of placement of a central venous cannula, a complication of surgery (injury to the airways, lung or diaphragm), or the use of excessively high pressures during positive pressure ventilation whilst under general anaesthesia. Pneumothoraces commonly necessitate additional procedures (pleural aspiration or inter-costal drain).

Patient relevance: Pneumothoraces cause the unpleasant symptoms of breathlessness and chest pain, may require additional invasive procedures and may contribute towards the development of respiratory failure with the consequences discussed above.

#### vi) Bronchospasm

Criterion: Newly detected expiratory wheezing treated with bronchodilators [43].

Clinical relevance: Perioperative bronchospasm may occur in patients with a background of asthma and or COPD (approx. 1.7% of such cases). Severe bronchospasm may prolong hospital length of stay and causes respiratory failure and increased mortality (approximately 2%).

Patient relevance: Bronchospasm is associated with dyspnoea and discomfort and as such is of relevance to patients. If severe, it may result in respiratory failure with the consequences discussed above.

#### vii) Aspiration pneumonitis

Criterion: Respiratory failure after the inhalation of regurgitated gastric contents [44].

Clinical relevance: Failure of airway protective mechanisms rarely occurs but when it does and gastric contents pass into the lungs the effects can be fatal. It is a recognised cause of acute respiratory distress syndrome (ARDS) and accounts for up to 30% of all deaths due to general anaesthesia. In less extreme examples it can contribute towards the development of respiratory failure.

Patient relevance: Aspiration pneumonitis is associated with respiratory failure. It is of relevance to patients as it may prolong hospital stay and increase mortality risk. Furthermore, it may result in uncomfortable sensations such as dyspnoea and invasive interventions such as non-invasive ventilation which may be associated with discomfort.

#### Secondary outcomes

- Each of the seven individual components of the composite primary outcome (defined using the European Society of Anaesthesiology and the European Society of Intensive Care Medicine [34]):
  - i) Respiratory infection
  - ii) Respiratory failure
  - iii) Pleural effusion
  - iv) Atelectasis
  - v) Pneumothorax
  - vi) Bronchospasm
  - vii) Aspiration pneumonitis
  - Postoperative ventilation;
    - Invasive ventilation;
    - Non-invasive ventilation (including continuous positive airway pressure (CPAP) and/or pressure support (BIPAP));
    - Optiflow (high flow nasal oxygen therapy);
    - o For non-invasive ventilation and high flow nasal oxygen therapy we will distinguish prophylactic use from use to treat a pulmonary complication;
  - Length of ICU stay;
  - Length of hospital stay;
  - Antibiotic prescription;
  - Bronchodilator prescription;
  - Patient reported outcomes (HRQoL questionnaires) (section6.3.4);
  - Change in maximal inspiratory pressure (MIP) from baseline;
  - Spirometry (forced expiratory volume, FEV1 and forced vital capacity, FVC) measurements from baseline;
  - Progression in training load (from baseline);
- 5.8 Mortality;
  - Other complications of surgery documented using the Clavien-Dindo [46] classification and the Comprehensive Classification Index [47, 48].

#### Sample size calculation

We will recruit 2,500 participants (1250 high resistance IMT, 625 low resistance IMT and 625 usual care), providing 90% power to detect a 5% difference in the primary outcome (of any PPC versus no PPC; 20% vs 15%, risk ratio 0.75) between high resistance IMT versus low

INSPIRE Protocol Version 2.0 resistance IMT and usual care combined. We do not anticipate a difference between the low resistance IMT and usual care groups and will be able to quantify a zero difference with a 95% CI of width +/-4.5%. The sample size required to achieve 80% and 90% power, assuming 5% statistical significance and a two sided test, for target differences of 8%, 5% and 3% are shown in Table 2. The primary outcome of any PPC (vs no PPC); assuming a PPC rate of 15% in the high resistance group and a PPC rate of 20% in the low resistance and usual care groups combined. In addition, the study will have 75% (90%) power to detect a difference of 15% (14%) versus 20% between the high intensity and low intensity groups, or between the high intensity and usual care groups.

**Table 2 Incidence of PPCs** 

|      | Incidence of PPCs                 | Risk ratio | •      | size (total)
ower |
|------|-----------------------------------|------------|--------|----------------------|
| IMT  | Low resistance IMT
/usual care |            | 90%    | 80%                  |
| 0.12 | 0.20                              | 0.6        | 928    | 708                  |
| 0.15 | 0.20                              | 0.75       | 2500   | 1890                 |
| 0.18 | 0.20                              | 0.9        | 16,368 | 12,278               |

By month 14 of the study (2 months before the end of the pilot phase, 6 months after the start of recruitment), we estimate that 160 participants will have been recruited to the IMT group and will have provided MIP at recruitment and before surgery. A sample of this size will allow a 0.53 SD difference in MIP between the two training strategies, to be estimated with a precision +/- 0.32 SD assuming a correlation of 0.5 between pre- and post-training measures.

#### 6.1 6. Study methods

#### **Description of randomisation**

Randomisation will be carried out after eligibility has been confirmed and consent given, and baseline measurements have been made. Randomisation will be performed by an authorised member of the local research team using a secure internet-based randomisation system ensuring allocation concealment. Participants will be randomised in a 2:1:1 ratio to: i) high resistance IMT ii) low resistance IMT or iii) usual care (no IMT and written instructions on deep breathing exercises). The random allocation will be stratified by centre and specialty, so that each speciality at each centre will have approximately equal numbers of participants allocated to the high resistance IMT group and low resistance IMT group/usual care. As the study is not evaluating the surgery per-se, surgical experience is not a criterion for participation (all participants will be under the care of a consultant surgeon). In the context of this study, clustering by surgeon is not relevant to the sample size and can be ignored (on the basis that the intraclass correlation is negligible; personal communication with [name] for a previous study).

In the SWAT (section 5.2), participants in the high resistance IMT group will be randomised in a 1:1:1:1 ratio to one of the four groups with random allocation stratified by centre and specialty.

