#### 5.6.3.1 Training participants in the high resistance IMT group

5.6.3Participants enrolled in the high resistance IMT group will have an initial face to face meeting (lasting up to 1 hour) with a research nurse or physiotherapist who has received training in how to deliver the IMT intervention (section 5.6.2). Participants will have FEV₁ and FVC readings taken with a spirometer and MIP measured using the POWERbreathe® KH2 device before being shown how the POWERbreathe® KHP2 device works, how to remove and clean the valve, how to breathe in and out correctly using the device, how to record their perceived exertion using an RPE rating scale [30, 31] and how to complete the paper training diary. The paper training diary will also include a comments section.

Participants will watch a training video during the face-to-face meeting which will provide stepby-step guidance on the correct use of the KHP2 device and on how to increase the training load in response to the participant's perceived exertion using the RPE rating scale. Participants will also be given written instructions to take home.

During the face to face appointment participants will undertake a supervised training session with the research nurse or physiotherapist of as many breaths as can be tolerated up to a maximum of 30 breaths (section 5.6.3.2). Participants will be coached by the research nurse or physiotherapist to maximise tidal volume by exhaling and inhaling fully for every breath of the training session. In addition, they will be encouraged to breathe IN as rapidly as possible, and to breathe OUT in a relaxed manner. This approach will maximise the training stimulus delivered to the inspiratory muscles.

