Participants in Phase 1 undertaking an additional face-to-face hospital visit within one week of starting IMT training will have MIP measured during the second visit using the POWERbreathe® KH2 device (ideally by the same person who performed the initial measurement), and their paper training diary and training load increments will be reviewed. Participants will undertake a supervised training session at this visit, during which their training technique will be reviewed and improved, as appropriate. Their perceived exertion rating (using the RPE scale) will be recorded immediately after this supervised session, and MIP will be recorded (pre- and post-training). Training data recorded by the POWERbreathe® KHP2 will also be extracted and recorded on the case report forms (CRF). The training load will be increased by 5% if any of the following conditions are met:

- i) MIP has increased;
- ii) the RPE rating is 5 or less at the additional visit;
- iii) the RPE rating recorded in the paper training diary during any of the previous two training sessions was 5 or less.

Patients will be instructed to continue to increase the training load over the next week, in response to their rating.

All high resistance IMT participants will be given a usual care leaflet containing advice on deep breathing exercises.

- 5.6.4 Low resistance IMT
- 5.6.4.1 Training participants in the low resistance IMT group

Participants enrolled in the low resistance IMT group will use an identical training device, but will use a different, low intensity, training protocol (see section 5.6.4.2). In their training session which will be delivered by a trained research nurse or physiotherapist, participants will have FEV1 and FVC readings taken with a spirometer and their MIP measured using the POWERbreathe® KH2 device before being shown how the POWERbreathe® KHP2 device works, how to remove and clean the valve and how to breathe in and out correctly using the

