6.3.1 Research procedures

#### Research assessments

Baseline assessments will be made before randomisation. Participants will be followed postoperatively to discharge, and at three months and six months post operatively. PPCs will be collected during hospital stay (section 5.7.1 for criteria for defining individual PPCs) using hospital notes and electronic databases. We will assess PPCs and adverse events and administer HRQoLs at three months and six months post-operatively. Follow-up for all participants at three and six months post-surgery will be by postal questionnaires, online completion using a secure login, or by telephone (participants will indicate their preferred method of follow-up). The local research team (or the co-ordinating centre, if deemed more appropriate) will contact participants at mutually agreed times.

INSPIRE Protocol Version 2.0

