- vii)Data relating to the participant's surgery, ICU stay and hospital stay (including any PPCs and any other adverse events) collected in all participating patients;
- viii) Additional tests and medications (e.g. bronchodilators, antibiotics) prescribed for all participating patients during their hospital stay;
- ix) Data on MIP and spirometry at the end of the intervention (when patient is admitted for surgery);
- x) Data on PPCs, any other adverse events and health status questionnaires collected at 3 months and at 6 months post-surgery for all participating patients.

To minimise bias, all PPCs have been defined as far as possible on the basis of objective criteria (section 5.7.1). To minimise bias, outcome measures are defined as far as possible on the basis of objective criteria. All personnel carrying out outcome assessment (with the exception of MIP measurements) will be blinded; this will minimise detection bias. The data collection schedule is shown in Table 3.

We will track patients for mortality for 6 months after surgery using hospital tracking systems or centrally collected data (Office for National Statistics).

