**Table 3 Data collection schedule** 

| Data item   | Baseline
(Pre-
randomisation) | Initial
training
visit'
High/low
resistance
IMT/usual
care groups | Additional
training
visit"
High
resistance
IMT group:
Phase 1
only | Pre-
surgery | In
hospital | Discharge | 3 months
post-
surgery | 6 months
post-
surgery |
|---|-------------------------------------|---|--|-----------------|----------------|-----------|------------------------------|------------------------------|
| Socio-demographic details   | ✓                                   |   |  |                 |                |           |                              |                              |
| Co-morbidities  | ✓                                   |   |  |                 |                |           |                              |                              |
| Routine CPET parameters#  |                                     |   |  | ✓               |                |           |                              |                              |
| Maximal inspiratory pressure (MIP)  |                                     | ✓   | ✓  | ✓               |                |           |                              |                              |
| Spirometry  |                                     | ✓   |  | ✓               |                |           |                              |                              |
| Check on adherence
and progression of
the IMT training
load § |                                     |   | √   | 1               |                |           |                              |                              |
| Routine clinical measures   | ✓                                   | ✓   |  | ✓               | ✓              | 1         |                              |                              |
| PPCs  |                                     |   |  |                 | ✓              | ✓         | ✓                            | ✓                            |
| Resource use schedule   |                                     |   |  |                 | ✓              | ✓         | ✓                     | ✓                            |
| SF-12   | ✓                                   |   |  | ✓               |                |           | ✓                            | ✓                            |

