# 6.14 Expenses

Participants in all three groups may require a minimum of one additional hospital visit before surgery to have their MIP recorded, and in the high and low resistance IMT groups to be given an IMT device and shown how to use it. We will try to coincide this visit with a pre-existing hospital appointment (e.g. the pre-operative assessment appointment) if this is more than two weeks before surgery.

Participants in the high resistance IMT group who are randomised in Phase 1 to one additional hospital visit to check the training load and IMT adherence may need an additional research visit which we will try to coincide with a pre-existing hospital visit if this falls between the start and end of the intervention period. Therefore, most participants will need an additional visit, a few may need two. Travel expenses will be provided for any visits made for the purpose of research only.

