**HADS** 

Connor Davidson Resilience Questionnaire

Self-efficacy using the Lorig self-efficacy questionnaire

Physical activity using the Duke Activity Status Index (DASI)

Each item is attributed a score from 1.75 to 8.0. If the answer is YES, the item score contributes to the total score. If NO, a score of 0 is added to the total score.

**MISSING**: 5 out of the 12 questions or less are reported, the DASI score would be considered missing or incomplete

Change in maximal inspiratory pressure (MIP)

Change in Spirometry (forced expiratory volume, FEV1 and forced vital capacity, FVC) measurements

= MIP on day of surgery – MIP at baseline

= Spirometry metric on day of surgery – spirometry metric at baseline

Mortality (in-hospital)

YES: Death recorded in hospital

NO: Participant was discharge from hospital

MISSING: otherwise

Mortality (to 30 days)

**YES:** Death recorded within 30-days following surgery

NO: Participant alive at 30-days following

surgery

Comprehensive Classification Index

MISSING: otherwise

Each Clavien-Dindo grade is assigned a weight. For instance, single complications are given weights as below:

Grade I: 8.7

Grade II: 20.9

Grade IIIa: 26.2

Grade IIIb: 33.1

Grade IVa: 42.1

• Grade IVb: 50.0

Grade V: 100.0

For multiples complications, the score is derived as the square root of the sum of all [(MRVphys × MRVpat)] and then divided by 2. This will provide a score between 0 and 100. The median (ratings are not normally distributed) reference value from physicians (MRVphys) and patients (MRVpat) for each grade are available at

http://links.lww.com/SLA/A405

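### The documents disagree on when the first MIP and spirometry are taken; as tabulated, the baseline for their change scores is measured after allocation, in a session run by staff who know the arm

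*Protocol*

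**What the plan says.** Protocol 6.1 and SAP 2.2 state: "Randomisation will be carried out after eligibility has been confirmed and consent given, and baseline measurements have been made". Protocol 6.3.1 agrees: "Baseline assessments will be made before randomisation". Protocol 6.6 also has each patient randomised once baseline data are in.

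The schedules differ. In protocol Table 3 and SAP Table 2 the MIP and spirometry rows are blank under the pre-randomisation baseline and ticked under the initial training visit, a column headed by the three allocated groups. The text on training fits the tables. Section 5.6.3.1 begins "Participants enrolled in the high resistance IMT group will have an initial face to face meeting" and takes FEV1, FVC and MIP at that meeting. Section 5.6.4.1 does the same for the low resistance arm: "In their training session which will be delivered by a trained research nurse or physiotherapist".

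On blinding, protocol 5.4.3 says everyone who assesses outcomes will be blinded, while 6.6 makes one exception: "All personnel carrying out outcome assessment (with the exception of MIP measurements) will be blinded". Protocol 6.2 says staff who administer IMT know the allocation.

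SAP 4.3.2 defines the MIP outcome as "MIP on day of surgery – MIP at baseline" and treats spirometry in the same way.

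**The concern.** A baseline is useful because allocation cannot have influenced it. MIP and spirometry depend on effort. If the first reading is taken once the arm is known, by someone who knows it, the reading can differ between arms for reasons unrelated to the patient's starting state, and a change score carries that difference into the result. Participants in the usual care arm also know that they have no device, so their own knowledge may matter in comparisons with that arm. A baseline tied to the training visit is also lost when that visit is missed.

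Change in MIP is the trial's evidence that high resistance training strengthened the inspiratory muscles and that low resistance training did not. Readers will use it to interpret whatever is found on pulmonary complications.

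**Working it through.** **1. The timings side by side**

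| Place | Timing given |
|---|---|
| Protocol 6.1, SAP 2.2 | Baseline measurements before randomisation |
| Protocol 6.3.1 and 6.6 | Baseline before randomisation |
| Protocol 6.3.2 (MIP), 6.3.3 (spirometry) | At the point of randomisation |
| Protocol 5.8 | MIP at recruitment |
| Protocol 1 | Inspiratory strength when the patient agrees to join |
| Protocol Table 3, SAP Table 2 | Initial training visit; pre-randomisation cell empty |
| Protocol 5.6.3.1, 5.6.4.1 | Within the arm's own training session, before the device is demonstrated |

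Nothing in either document reconciles these. A slip confined to the table is unlikely, because 5.6.3.1 and 5.6.4.1 say the same. The SAP cites protocol v3.0 and its Table 2 was edited: the MIP tick at the additional SWAT contact, present in protocol Table 3, is gone. The training-visit ticks were kept.

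**2. Who measures, and who knows what**

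Protocol 5.6.2 trains the same staff, ideally one or two per site, to measure MIP and to teach IMT. Section 6.2 says those who deliver IMT are not blind. Section 6.6 exempts MIP from blinded assessment but not spirometry, although both are taken in the same session. Section 5.4.3 exempts neither.

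**3. The one stated figure that rests on baseline MIP**

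Protocol 5.8 gives a precision of ±0.32 SD for a 0.53 SD difference in MIP between two training strategies, with 160 participants and a pre-post correlation of 0.5. With 80 per strategy:

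- Half-width = 1.96 × √(2/80 + 0.53²/(2 × 160)) = 1.96 × √(0.02500 + 0.00088) = 0.315, which rounds to the stated 0.32.
- Without the 0.53² term, a change score has SD √(2(1 − 0.5)) = 1, so 1.96 × √(2/80) = 0.310.
- A baseline-adjusted analysis has residual SD √(1 − 0.5²) = 0.866, so 0.866 × 0.310 = 0.268.

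The figure reproduces and is not the smaller one that baseline adjustment would give. It does not settle the timing.

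**4. How a baseline error would carry through**

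Let b be the between-arm difference in baseline error, in SD units. The documents give no value for b and no SD for MIP, so the values below are assumptions. The adjusted column also assumes equal SDs before and after training.

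| b (assumed) | Shift in change-score contrast, b | Shift in baseline-adjusted contrast, 0.5b |
|---|---|---|
| 0.10 | 0.10 | 0.05 |
| 0.25 | 0.25 | 0.125 |
| 0.50 | 0.50 | 0.25 |

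A comparison of pre-surgery values alone is free of b.

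**5. Lost baselines**

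The progression criteria in protocol 5.2.6 tolerate up to 10% not starting the allocated intervention. This is a tolerance, not a forecast. If 10% of the 160 lacked a baseline, 144 would remain and the half-width would be 1.96 × √(2/72 + 0.53²/(2 × 144)) = 0.332. If 10% of one arm were missing and differed from the rest by 0.25 to 1.0 SD (assumed), that arm's mean would shift by 0.10 × 0.25 = 0.025 to 0.10 × 1.0 = 0.10 SD.

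**6. Where it enters the results**

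SAP 4.4.3 models only the main primary outcome and the SWAT primary outcome. MIP and spirometry are tabulated without estimates of the difference. Table A10 shows baseline, day-of-surgery and change values for the SWAT groups. Table A11, which covers the trial arms, lists only the change.

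**The case against.** The strongest reply is that the documents do not establish that the measurements were taken after allocation. Protocol 1, 5.8, 6.3.2 and 6.3.3 can all be read as placing them at or before randomisation, and 6.1 says so of baseline measurements in general. That stands, and is why this is a contradiction to resolve rather than a proven fault. It could also be said that baseline in 6.1 means only history and questionnaires. Then 6.1 and the tables agree, but post-allocation measurement becomes the design, and 6.3.2, 6.3.3 and 5.8 still differ from the tables.

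There are safeguards. MIP comes before the device is shown, staff training is standardised, at least five efforts are required, and high and low resistance participants are meant to be masked from each other. These lower the risk. The repeatability rule limits scatter within a person, however; it does not equalise effort between arms.

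A reader might infer more than the documents support:

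- **Coached MIP tests.** The coaching in 5.6.3.1 concerns training breaths. No text describes coaching of the test. Nor do the documents say who measures usual care participants, or exactly when participants learn whether they have a device.
- **A size for the bias.** The 5 cm H2O limit in 6.3.2 applies to a person's best three readings; it is not a shift between arms. The 0.53 SD in 5.8 compares training strategies within the IMT group, so it is not a yardstick for differences between trial arms.
- **An effect on the primary analysis through pooling.** Protocol 7.1.2 sets a 0.25 SD limit on MIP but does not say whether it means change or level. SAP 4.4.1 drops the step.
- **A measurement-only visit for usual care.** Protocol 6.14 says "Participants in all three groups may require a minimum of one additional hospital visit before surgery to have their MIP recorded", which is conditional, and 6.4 describes face-to-face training in all three arms.
- **A biased SWAT result.** Starting load is set from MIP (5.6.3.2) and load change starts at the training visit (SAP 4.3.2). The link is indirect, lies within one arm, and has no size that the documents can supply.

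SAP 4.6 already footnotes missing continuous data and looks into reasons where missingness differs between groups. That covers part of the missing-baseline point.

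**Conclusion.** The contradiction is real and should be corrected. If the tabulated schedule was followed, the baseline in the MIP, FEV1 and FVC change scores is a post-allocation measurement. It is open to assessor influence, to participant knowledge in comparisons with usual care, and to loss when the training visit is missed. Spirometry taken in that session also conflicts with the blinded-assessment statement in protocol 6.6.

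Bias is a risk and has not been shown. Its size cannot be derived from the documents, and the shifts worked out above rest on assumed values. If the measurements did precede randomisation, the bias concern falls away, and Table 3, SAP Table 2, 5.6.3.1 and 5.6.4.1 are what need correcting.

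Under the SAP the consequence is confined to descriptive MIP and spirometry tables. The primary analysis of pulmonary complications does not use these measurements.

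**What to change.** **Protocol (for the record and any successor trial).** Move the first MIP and spirometry ticks in Table 3 to the pre-randomisation baseline. Require both to be completed and entered before the web system releases the allocation. Align 5.6.3.1, 5.6.4.1, 6.3.2 and 6.3.3. The small downside is that randomisation must follow the measurement at that visit.

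**SAP.** The funder confirmed closure in May 2022 (SAP 1.1.2) and the SAP in hand is v0.3 of July 2024, so moving the tick in Table 2 could misdescribe the data. Instead:

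- state when the first MIP and spirometry were actually taken;
- add their timing relative to randomisation to Table A9, which is already to be repeated by allocation, and show missing baselines by arm;
- show pre-surgery values beside the changes in Table A11, as Table A10 already does;
- caveat change scores whose baseline was taken after allocation.

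The cost is a few lines of text and some table rows, provided measurement dates were recorded. If they were not, the SAP should say that the timing is unknown. Pre-surgery values avoid the baseline problem, but for MIP they are still exempt from blinded assessment, and the caveat should say so.
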